## **9.5. Treatment of Overdose**

This cohort study will not provide or recommend any treatment. Patients' diagnosis and treatment will be left to their physicians' judgement and routine practice. Thus, this section is not applicable.

## **9.6. Safety Assessments**

This cohort study will not provide or recommend any treatment. No safety assessment is scheduled.

## **9.7. Pharmacokinetics**

PK parameters are not evaluated in this study.

## **9.8. Pharmacodynamics**

Pharmacodynamic parameters are not evaluated in this study.

## **9.9. Genetics**

Genetics are not evaluated in this study.

## 10. STATISTICAL CONSIDERATIONS

### 10.1. Sample Size Determination

#### 10.1.1. Hypotheses

This study is mainly descriptive with no formal inference associated with the study objectives. Confidence intervals will accompany all effect estimates.

#### 10.1.2. Study Design Considerations

This is a longitudinal study in subjects with COPD and controls. The follow-up period is 2.5 years with scheduled clinic visits at study entry, 6 months, 18 months, and 30 months.

#### 10.1.3. Sample size Considerations

Sample size was decided based on practical consideration; however, some justification of GOLD I and II Grades and for sample size for all COPD patients is provided below.

There is no formal inference planned, meaning no powered hypothesis test for overall study will be performed. Sample size justification is based on precision of effect estimates for rate of decline in FEV1 over 2.5 years.

A review of data from Study HZC113782 FEV1 was collected at 3-month intervals on moderate COPD subjects suggests that a within subject standard deviation (model based residual error estimate) as 155 mL, and a standard error of the rate of decline in FEV1 as 2.5 mL/year from placebo group. Those variability estimates were increased to 50% higher as 233 mL and 3.8 mL/year, respectively, for the following sample size calculation; this is mainly based on the consideration that a more heterogeneous study population and non-drug interventional cohort nature by design will yield higher variability comparing to those observed in a randomized clinical trial.

To make simple calculation, it is assumed within subject's standard deviation and standard error of the rate of decline in control groups (Chronic Bronchitis, Healthy Control) are the same as the assumption for COPD subjects.

To detect a difference of  $\Delta$  units between the mean rate of decline in two groups, Schlesselman [Schlesselman, 1973] proposed the following formula to calculate  $N$ ,

$$N = [2(Z_{\alpha/2} + Z_{\beta})^2 \{\hat{\sigma}_{\beta}^2 + 12(P-1)\hat{\sigma}^2/[D^2P(P+1)]\}]/\Delta^2$$

where  $\hat{\sigma}_{\beta}^2$  is an estimate of the variance associated with the rate of decline in FEV1,  $\hat{\sigma}^2$  is an estimate of the variation about the regression line within a person,  $D$  is the duration of the study,  $P$  is the number of measurements collected during the study,  $Z_{\alpha/2}$  is the upper  $(1 - \alpha/2)$  critical value for the standard normal distribution, and  $Z_{\beta}$  is the upper  $(1 - \beta)$  critical value for the standard normal distribution. It can be adapted to determine  $N$  for a

$100(1 - \alpha)\%$  two-sided confidence interval for the difference between the rates of decline in  $FEV_1$  of two groups that has precision  $\Delta$  as

$$N_1 = Z_{\alpha/2}^2 \hat{\sigma}_p^2 (r + 1) / (r \Delta^2)$$

where  $\hat{\sigma}_p^2 = \hat{\sigma}_\beta^2 + 12(P - 1)\hat{\sigma}^2 / [D^2 P(P + 1)]$ ,  $r = N_2/N_1$ , and  $N_1$  and  $N_2$  are the sample sizes associated with each of the two groups.

In this study, it is planned to collect  $P=4$  measurements of  $FEV_1$  over  $D=2.5$  years. One of interest is an estimate of the rate of decline in  $FEV_1$  between subjects GOLD I and II.

Under the above assumptions with 95% confidence and a 25% drop out, the following table gives sample sizes necessary to attain the levels of precision of Gold I vs. Gold II comparison.

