### 10.2.3.1. Main Cohort

- Change from baseline and Rate of decline in FEV1 in millilitres (mL):

Descriptive statistics of FEV1 and change from baseline FEV1 will be reported for baseline and all subsequent visits. The raw mean change from baseline at each visit will be presented graphically.

Rates of decline in FEV1 will be estimated for each type of COPD subjects, overall COPD subjects, chronic bronchitis group and healthy control group.

In order to obtain rate of decline in FEV1, particular from a mixed effects model, a random coefficients model, will be used. FEV1 after baseline will be fitted as the response variable with the proposed selection of predictors including type of subjects (i.e. GOLD I-IV, chronic bronchitis, healthy control), age, gender, smoking status, baseline FEV1, count of COPD exacerbations, site, time on study and type of subjects by time interaction. Participants and time on study will be random effects. Further details will be included in RAP.

Rates of decline in other endpoints may also be estimated in a similar fashion, if warranted.

- Rate of moderate/severe exacerbations:

Exacerbations separated by less than 7 days will be treated as a continuation of the same exacerbation. The exacerbation frequency, type and duration will be summarized using descriptive statistics for Full population.

A generalized linear model assuming the negative binomial distribution will be used to analyze the exacerbations rate among different type of subjects. Additional methods including time to event analysis will be considered as appropriate.

- Change from baseline in CAT score:

CAT score and change from baseline value will be summarized using descriptive statistics for the Full population.

If appropriate, Mixed Models Repeated Measures (MMRM) model will be used to analyze CAT score among different type of subjects.

- Clinically important deterioration (CID) components:

CID will be summarized for Full population using descriptive statistics.

If data permit, generalized linear mixed model will be used to analyze CID among different type of subjects and time to CID will be assessed using time to event models.

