## **Clinical feature Analyses (Chapter 8)**

Spirometry at each planned visit (baseline, Month 6, Month 18 and Month 30) and the post-baseline change from baseline will be summarised. FEV1 and FVC will be analysed using MMRM model. Analysis window for post-baseline visits of spirometry is defined as planned visit date  $\pm 90$  days. Spirometry results out-of-window will be regarded as missing.

Rate of change (decline) in FEV1 and FVC (yearly, unit ml/year) will be analysed at the end of study. All results regardless of the visit window will be included in the analyses.

COPD GOLD grade change, as the result of change of spirometry. Spirometry results out-of-window (visit window is  $\pm 90$  days) will be regarded as missing.

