
 
• Least-square (LS) means and LS mean change from baseline values for each arm at each visit will be presented with their associated standard errors as well as 95% CIs.
 
• The LS mean differences and their associated standard errors (and associated 95% CIs) compared with Health Control for all visits will be presented in tables. Nominal P value will be presented just for reference.
 

Yearly rate of change (mL/year) in FEV1 and FVC will be summarized and analysed using random coefficients models respectively. The model is described in the following table.

Endpoint / Variables

 
• Rate of change in FEV1 in mL/year
 
• Rate of change in FVC in mL/year
 

Model Specification

 
• Random coefficients model
 
• For the analyses of rate of decline, each subject's actual time on study will be used, rather than assigning visit as a categorical variable.
 

- While missing data are not explicitly imputed in the mixed effects model, there is an underlying assumption that the data are missing at random. Participants and time on study will be random effects.
- Terms in the model:
  - **Response:** FEV1 or FVC at each visit.
  - **Population:** Full population
  - **Categorical:** type of subjects (i.e. GOLD I-IV, chronic bronchitis, healthy control), gender, smoking status, site (type of hospital), maintenance treatment (Y/N) and ICS containing (Y/N), Childhood chest disease (Y/N) and biomass fuel exposure (Y/N)
  - **Continuous:** age, baseline FEV1, count of COPD exacerbations, time on study
  - **Interaction:** type of subjects \* time on study
- Models will be fitted for pre- and post-bronchodilator FEV1 or FVC, respectively.
- The model will be fitted with an unstructured variance-covariance matrix. If the model fails to converge, then alternative covariance structures may be investigated.
- A subject needs to have at least one post-baseline value to be included in the analysis.

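### The planned precision for FEV1 decline uses a group standard error as the person-level slope SD and counts a baseline value that the protocol's own model excludes

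*Protocol*

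**What the plan says.** Protocol 10.1.3 states that "Sample size was decided based on practical consideration" and then supports the number by the precision of the rate of FEV1 decline. From an earlier study it takes a residual within-subject SD of 155 mL and "a standard error of the rate of decline in FEV1 as 2.5 mL/year from placebo group". Both are raised by 50%, to 233 mL and 3.8 mL/yr, and entered in the formula for σ_p². There σ_β² "is an estimate of the variance associated with the rate of decline in" FEV1, and P = 4 measurements are taken over D = 2.5 years. With 525 completers per group (700 enrolled, 25% dropout), Table 2 gives a half-width of 15 mL/yr for GOLD I against GOLD II. With 1,275 COPD completers the total width is 13.7 mL/yr.

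Protocol 10.1.2 lists "scheduled clinic visits at study entry, 6 months, 18 months, and 30 months". In the rate-of-decline model of Protocol 10.2.3.1, FEV1 "after baseline will be fitted as the response variable with the proposed selection of predictors". Baseline FEV1 is one of those predictors, and participant and time are random effects.

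SAP 8.1 gives the response as FEV1 "or FVC at each visit" and lists as continuous covariates "age, baseline FEV1, count of COPD exacerbations, time on study". SAP 2.2.1 counts baseline as a visit: "Spirometry at each planned visit (baseline, Month 6, Month 18 and Month 30". Section 7.4.1 of the earlier RAP restricted the response to post-baseline values, but SAP 8.1 no longer carries that sentence.

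**The concern.** The formula adds σ_β² to the within-person slope variance and only then divides by N, so σ_β must be the SD of individual participants' slopes. The standard error of a placebo group's mean slope is a different quantity: it has already been divided by the square root of that group's size.

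The formula also credits each participant with a baseline measurement. Under Protocol 10.2.3.1 that measurement is a predictor, so it does not contribute to the slope as a response.

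Both errors make the planned intervals look narrower. These figures are the protocol's only statement of what 700 participants per GOLD I and II arm can show about FEV1 decline.

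The open wording in SAP 8.1 matters beyond width. If Visit 1 FEV1 is a response, it is also a covariate in the same model and, through the screening assessment in SAP 17.5.2, the basis of the GOLD arms. That risks regression to the mean in the arm slopes. The documents do not allow its size to be computed.

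**Working it through.** **Inputs.** z = 1.96; σ = 233 mL (155 × 1.5); σ_β = 3.8 mL/yr (2.5 × 1.5); P = 4; D = 2.5; 525 completers per arm; 1,275 COPD completers. Visits fall at 0, 0.5, 1.5 and 2.5 years.

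**Reproducing the plan.** σ_p² = σ_β² + 12(P−1)σ²/[D²P(P+1)].

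- 12 × 3/(6.25 × 20) = 0.288 = 1/3.47, where 3.47 is the time sum of squares of four equally spaced visits.
- σ_p = √(3.8² + 0.288 × 233²) = 125.1, as stated. With σ_β = 0 it would be 125.04, so 3.8 was entered directly as an SD.
- Half-width = 1.96 × 125.1 × √(2/525) = 15.1 (stated 15).
- Total width = 2 × 1.96 × 125.1/√1275 = 13.7 (as stated).

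The arithmetic is sound. The fault lies in the inputs and in the model they describe.

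**The slope SD.** 3.8²/125.1² = 0.09% of the variance. Read as a person-level SD, 3.8 puts 95% of true slopes within 1.96 × 3.8 = 7.4 mL/yr of the mean, which amounts to almost no variation between people. The protocol's own standard error for the all-COPD mean slope is 125.1/√1275 = 3.5 mL/yr, the same size as this input. That fits the group-level label but does not prove it.

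**The response.** For actual visit times, σ_p² = σ_β² + σ²/SS, where SS is the sum of squared deviations of visit time from its mean.

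| Response (233 mL, σ_β = 3.8, completers) | SS | σ_p | GOLD I vs II half-width | All-COPD total width |
|---|---|---|---|---|
| Protocol formula | 3.47 | 125.1 | 15.1 | 13.7 |
| Four visits, real times | 3.6875 | 121.4 | 14.7 | 13.3 |
| Three post-baseline visits | 2.0 | 164.8 | 19.9 | 18.1 |

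Unequal spacing is therefore harmless; losing the baseline response is what widens the interval, by about 32% (164.8/125.1 = 1.32). Adjusting for baseline FEV1 does not recover the loss: simulating the post-baseline model with that covariate, 525 per arm, gave 19.9. A half-width of 15 would need 1.96² × 164.8² × 2/15², or 928 completers per arm.

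**Dropout.** For the post-baseline response:

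- No dropout (700 per arm, 1,700 COPD): 17.3 and 15.7.
- 25% leaving evenly after Visits 1, 2 and 3, partial data used (assumed pattern; intercept SD assumed 150 to 600 mL): 19.2–19.6 and 17.4–17.8.

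**Slope SD range (assumed; not in the documents).** GOLD I vs II half-width, completers, 233 mL:

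| Slope SD (mL/yr) | 25 | 50 | 75 | 100 |
|---|---|---|---|---|
| Four real visits | 15.0 | 15.9 | 17.3 | 19.0 |
| Post-baseline only | 20.2 | 20.8 | 21.9 | 23.3 |

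A half-width of 15 requires σ_p ≤ 15/(1.96 × √(2/525)) = 124.0. With four real visits in completers the slope SD may then reach √(124.0² − 233²/3.6875) = 25.5 mL/yr. With post-baseline values only, the residual term alone (233/√2 = 164.8) already exceeds 124.0.

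**Uninflated residual.** At 155 mL the post-baseline response gives 13.3 and 12.0, and 15 is met up to a slope SD of √(124.0² − 155²/2) = 58 mL/yr.

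**Protocol 10.1.4.** The section calls 250 an SD of the rate of decline in mL/year. Its width of 14.7 reproduces only if 250 is the residual SD in mL: √(3.8² + 0.288 × 250²) = 134.2, and 2 × 1.96 × 134.2/√1275 = 14.7. As a slope SD, 250 would give 30.7.

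**The case against.** The strongest reply is that nothing turns on these figures. N was fixed on practical grounds, no test is powered, and the reported intervals will come from the data. This stands, and it is why N should not change. The section nevertheless offers precision as its justification, so that precision should belong to the planned model.

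Second, Protocol 10.2.3.1 defers details to the RAP, and the current SAP can be read as using all four visits, in which case the stated figures hold. With partial data they hold more comfortably: on the dropout assumptions above, four visits give about 14.2 to 14.4, and 15 is then exceeded only above a slope SD of roughly 40 mL/yr rather than 25.5. This stands for that reading. It does not rescue the figures under Protocol 10.2.3.1, and SAP 8.1 retains baseline FEV1 as a covariate without saying whether Visit 1 is a response.

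Third, 2.5 could be an SD mislabelled as a standard error, which would make this part a wording slip. Nothing in the documents says so, but the numerical effect cannot be fixed without the reference study's random-slope SD.

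Fourth, the 50% inflation leaves a margin. At 155 mL even the post-baseline reading meets the stated figures for modest slope SDs. This also stands, but the protocol itself chose 233 mL as its planning value.

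Finally, SAP 8.1 presents slope differences against healthy controls and does not list the GOLD I against GOLD II difference that Table 2 sizes. This limits the practical weight of Table 2 but does not make it correct.

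**Conclusion.** The concern holds. As written, Protocol 10.1.3 uses a quantity it labels a group standard error where a between-person SD is required, and its precision does not match the model in Protocol 10.2.3.1. At 233 mL and 3.8 mL/yr with completers, that model gives a half-width of 19.9 mL/yr rather than 15 and a total width of 18.1 mL/yr rather than 13.7; a larger slope SD widens both. If SAP 8.1 means that all four visits are responses, 14.7 and 13.3 apply, and the stated figures survive for a small slope SD.

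The response effect follows from the documents alone. The effect of the slope SD is known in direction only, and the 25 to 100 mL/yr range is assumed. The consequence is overstated planning precision, together with a modelling choice that the current SAP leaves open. It should be corrected, but it does not threaten the sample size.

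**What to change.** Keep N.

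1. In SAP 8.1, state whether Visit 1 FEV1 is a response. Post-baseline only would match Protocol 10.2.3.1 and the earlier RAP 7.4.1. If Visit 1 is kept as a response, say how it can also be a covariate and define the GOLD arms.
2. In Protocol 10.1.3, replace 3.8 with the between-subject (random-slope) SD from the same reference study, and name its source.
3. Restate Table 2 and the 13.7 mL/yr width for the chosen model at the actual visit times. At 233 mL with completers, expect about 20 and 18 mL/yr or wider for post-baseline only, or about 14.7 and 13.3 or wider for four visits.
4. In Protocol 10.1.4, call 250 the residual SD in mL.

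The cost is wording in the protocol and SAP, with no extra participants or visits. The stated precision may become less favourable.

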**Table 2      Sample size for Gold I vs. Gold II under given precision**

| Interested comparison             | Precision*
(ml/yr) | Subgroup | Completers | Total sample size
including 25%
drop out |
|-----------------------------------|-----------------------|----------|------------|--|
| Gold I vs. Gold II
$r = 1 : 1$ | 15                    | Gold I   | 525        | 700  |
|                                   |                       | Gold II  | 525        | 700  |

\*: half width of a 95% confidence interval

Based on the total completed  $N = 1275$  COPD subjects, a 95% two-sided confidence interval for the rate of decline in  $FEV_1$  of all COPD subjects will have a total width of

$$W = 2 \times Z_{\alpha/2} \times \hat{\sigma}_p / \sqrt{N} = 2 \times 1.96 \times 125.1 / \sqrt{1275} = 13.7 \text{ ml/year}$$

$$\text{where } \hat{\sigma}_p = \sqrt{\hat{\sigma}_\beta^2 + 12(P - 1)\hat{\sigma}^2 / [D^2 P(P + 1)]} = 125.1$$

#### 10.1.4.    Sample Size Sensitivity

The width of any confidence interval will be wider than expected, if the true standard deviation of an endpoint is larger than assumed. For example, if the within subject standard deviation of the rate of decline in  $FEV_1$  is 250ml/year, then the 95% confidence interval for COPD subjects overall rate of decline in  $FEV_1$  will have width 14.7ml/year. Conversely, actual standard deviations that are smaller than assumed will result in narrower confidence intervals.

### 10.1.5. Sample Size Re-estimation

Sample size maybe re-estimated during the conduct of study.

## 10.2. Key Elements of Analysis Plan

The high-level analytic approaches and methods are described for each objective. Further details and exploratory analyses will be described in the Reporting and Analysis Plan (RAP).

### 10.2.1. Populations for Analyses

For purposes of analysis, the following populations will be defined:

| Population            | Description   |
|-----------------------|---|
| Full population       | The Full Population will consist of all subjects who are enrolled in the study and attend Visit 1.                                    |
| Sub-cohort population | Subjects who are enrolled in the Biomarker & Digital sub-cohort and who provided a least one additional sub-cohort assessment.        |
| Completer Population  | The Completer Population will consist of all subjects in the Full Population who complete all scheduled clinic visits over 2.5 years. |

Other sub-populations may be defined based on disease severity, co-morbidities, age, gender, or subject phenotypes. This will be detailed in RAP.

### 10.2.2. Descriptive Analyses

Each endpoint collected during the study that represents a continuous measure will be summarized with descriptive statistics with mean, median, min, max and SD at each clinic visit as actual values and as change from baseline (Visit 1), if appropriate. Endpoints that are discrete in nature will be summarized as frequencies and percentages at each clinic visit. Counts (e.g. exacerbations of COPD) will be expressed as event rates per person-year.

mMRC dyspnea score will be summarized using descriptive statistics for the Full population. Wilcoxon-rank sum test will be used to analyse mMRC dyspnea score among different type of subjects, if data permit.

SGRQ-C score will be transformed into SGRQ score and summarized using descriptive statistics.

### 10.2.3. Disease Progression Analyses

Disease progression in clinical, radiological and biological measurements will be described based on longitudinal data.

### 10.2.3.1. Main Cohort

- Change from baseline and Rate of decline in FEV1 in millilitres (mL):

Descriptive statistics of FEV1 and change from baseline FEV1 will be reported for baseline and all subsequent visits. The raw mean change from baseline at each visit will be presented graphically.

Rates of decline in FEV1 will be estimated for each type of COPD subjects, overall COPD subjects, chronic bronchitis group and healthy control group.

In order to obtain rate of decline in FEV1, particular from a mixed effects model, a random coefficients model, will be used. FEV1 after baseline will be fitted as the response variable with the proposed selection of predictors including type of subjects (i.e. GOLD I-IV, chronic bronchitis, healthy control), age, gender, smoking status, baseline FEV1, count of COPD exacerbations, site, time on study and type of subjects by time interaction. Participants and time on study will be random effects. Further details will be included in RAP.

Rates of decline in other endpoints may also be estimated in a similar fashion, if warranted.

- Rate of moderate/severe exacerbations:

Exacerbations separated by less than 7 days will be treated as a continuation of the same exacerbation. The exacerbation frequency, type and duration will be summarized using descriptive statistics for Full population.

A generalized linear model assuming the negative binomial distribution will be used to analyze the exacerbations rate among different type of subjects. Additional methods including time to event analysis will be considered as appropriate.

- Change from baseline in CAT score:

CAT score and change from baseline value will be summarized using descriptive statistics for the Full population.

If appropriate, Mixed Models Repeated Measures (MMRM) model will be used to analyze CAT score among different type of subjects.

- Clinically important deterioration (CID) components:

CID will be summarized for Full population using descriptive statistics.

If data permit, generalized linear mixed model will be used to analyze CID among different type of subjects and time to CID will be assessed using time to event models.

### 10.2.3.2. Sub-cohort

General summary/analysis information for each sub-cohort endpoints are listed as below. More details will be included in RAP.

- EXACT events: the analysis will summarize N of events, their onset, duration and severity. EXACT events will be derived according to the EXACT manual [Leidy, 2013] with any alternative considerations detailed in the RAP.

- E-RS: COPD total and domain scores: each 4-week interval summary/analysis will be done. If data permit, mean weekly scores will be considered for the analysis; this assumption will be tested prior starting data analysis. Relationships between mean E-RS scores and other study variables will be evaluated using a range of analysis of variance and analysis of covariance. Changes from baseline in Total and domain scores at pre-defined time points will be analysed using a mixed model for repeated measures, adjusted for baseline E-RS scores and other key variables.

CCI

- 
- Daily Activity: summary/analysis with appropriate statistics will be done based on the data extracted from wrist band.

